## **METHODS:**

**Overview:** We will conduct a pilot feasibility trial of 40 women Veterans of reproductive age with mental illness receiving outpatient mental health services at the VA Maryland Health Care System (VAMHCS). Participants will be randomly assigned to 1) the RLP-MH intervention or 2) control (receipt of the VA's Reproductive Life Planning Quick Guide and other written materials) after completion of the baseline assessment. The purpose of this pilot trial is to establish feasibility and acceptability of the RLP-MH and to explore its potential efficacy.

**Participants:** Forty participants will be recruited from VAMHCS outpatient mental health and women's health programs (Baltimore & Perry Point VAMCs; CBOCs). Inclusion criteria are: (1) female, 2) between 18 and 40 years of age, (3) chart diagnosis of schizophrenia or schizoaffective disorder, bipolar disorder, major depression, or PTSD, and (4) currently receiving mental health services at the recruitment site. Exclusion criteria are: (1) currently pregnant, or (2) inability to have children (e.g. infertility, hysterectomy, tubal ligation).

**Recruitment:** Recruitment will take place at outpatient clinics/programs within the VA Maryland Health Care System (VAMHCS). Potential VA participants will be identified by several methods: (1) CPRS chart review and screening via use of a partial HIPAA waiver, (2) VA clinician referrals of participants who meet inclusion criteria and who might be interested in participating, (3) Self referrals by participants who hear about the study and are interested in participating or who have participated in other MIRECC studies and have given permission to be contacted regarding future studies, (4) Self-referral via IRB approved study flyer and other advertisements. Per VA requirements, initial contact with potential veteran participants will be made in person or by letter prior to any telephone contact. Specifically, we will approach individuals before or after their VA appointments.

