**STATISTICAL ANALYSIS PLAN:**

Overview: Consistent with the objectives of this small pilot randomized controlled trial (RCT), our primary data analysis approach will be to estimate means, proportions, and group differences with point and interval estimation (i.e. 95% confidence intervals). In the face of sample variation, a confidence interval provides a range for the "true" population value of a parameter consistent with the observed data. Further, estimates of recruitment, completion, and attrition percentages will be used to plan for a larger trial if warranted. We will estimate difference of means (and effect sizes) and proportions on outcomes to evaluate potential for efficacy as another input to the decision whether the RLP-MH intervention merits further testing. The trial will be conducted according to the "intent-to-treat" principle in that outcomes will be assessed regardless of RLP-MH attendance.

**Aim 1 - Feasibility:** We will calculate point and interval estimates of the overall recruitment percentage and the RLP-MH intervention completion percentage (defined as attending baseline visit and the one-month follow-up visit). The point estimate for overall recruitment percentage = number consented / number approached to participate in the trial. Interval estimation will be by 95% confidence intervals. The point estimate for the RLP-MH completion percentage = number completed / number randomized to the intervention. The overall and group attrition percentages

will also be estimated, = number without the 2-month assessment / number consented and randomized. Interval estimation will be by 95% confidence intervals. In addition to assessing feasibility, these estimates will also inform the planning of a subsequent confirmatory trial if warranted. Point and interval estimates will be calculated to estimate mean fidelity score to further assess feasibility.

Aim 2 – Acceptability: Acceptability of the RLP-MH intervention will be assessed quantitatively and qualitatively. Quantitatively, we will calculate point and interval estimates of our satisfaction questionnaire. Responses to open-ended acceptability questions at the post-treatment assessment will be compiled and examined for common themes.

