Aim 3 – Explore Potential Efficacy: Preliminary. Before we perform analyses, we will first check variable distributions and missing data. Despite randomization, with a smaller sample size it is possible for covariate imbalance to occur by chance. As a sensitivity analysis, when making group comparisons, if a clinically relevant covariate (e.g. age, race) significantly differs across the two conditions we will repeat the primary analysis adjusting for the covariate to assess its impact on outcome effects as a secondary analysis.

3a: For the three outcomes for this sub-aim, the Decisional Self-Efficacy, Attitudes Towards RLP, and RLP Behavioral Intentions scales we will estimate the difference in mean change from baseline to the 2-month follow-up between the RLP-MH and control groups using a simple random intercept linear mixed model. This will allow inclusion of all observed outcome data. Between-group effect sizes will be calculated as the model-estimated difference in mean change divided by baseline pooled (across interventions) raw standard deviation. A bootstrap procedure will be used for effect size interval estimation. In addition to the comparisons between groups above, we will estimate the mean change in the RLP-MH condition on the RLP Behavioral Intentions and Decisional Self-Efficacy Scales from baseline to post-intervention using a mixed model.

3b: The RLP behaviors that will be quantitatively analyzed are generally Yes/No self-report questionnaire items that will be assessed at the 2-month follow-up in both arms of the trial. For example, questions ask: (1) if they've had any patient-provider reproductive health discussions, (2) if they've sought after reproductive health information, and (3) if they've taken any steps to address their reproductive needs or goals. We will estimate the group difference in the proportion of 'Yes' responses with point and interval estimates using normal approximation. To adjust for a potential out-of-balance covariate (e.g. race) we will use logistic regression.

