Sample size considerations: With an interval estimation approach, sample size is reflected in the precision of these estimates (i.e. the larger the sample the smaller the confidence interval widths). For example, for feasibility (Aim 1), with the proposed sample size of 20 randomized per study arm, observed intervention completion proportions in the RLP-MH group of .60, .75, and .90 would have 95% confidence intervals of (.39,.81), (.56,.94), and (.77,1.00). For potential efficacy assessed at the 2-month follow-up (Aim 3b), one assessed health behavior outcome will be "Any conversations with health provider regarding RLP or reproductive health? Yes/No". If the proportions of Yes responses to this question in the RLP-MH and control condition are, respectively, .25 and .10, .50 and .20, or .60 and .20, then the point estimates for the difference would be .15, .30, and .40, favoring RLP-MH, and the 95% confidence intervals for the differences would be (-.08,.38), (.02,.58), and (.12,.68). These calculations account for attrition equal to 15%.

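### The Aim 3b planning intervals are said to allow for 15% attrition but are computed on all 20 per arm; at 17 per arm all three widen and the middle one reaches zero

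*Combined protocol and SAP*

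**What the plan says.** In the Statistical Analysis Plan, under Sample size considerations, precision is illustrated "with the proposed sample size of 20 randomized per study arm". That agrees with the total of 40 in the Methods overview.

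For Aim 3b the example outcome is whether the participant had any conversation with a provider about reproductive health, assessed at 2 months. The assumed Yes proportions in RLP-MH and control "are, respectively, .25 and .10, .50 and .20, or .60 and .20". For these, "the 95% confidence intervals for the differences would be (-.08,.38), (.02,.58), and (.12,.68"). The paragraph closes with "These calculations account for attrition equal to 15" percent.

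Two other parts of the SAP fix how the figures should be obtained:

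- Aim 3b gives the method: "We will estimate the group difference in the proportion of 'Yes' responses with point and interval estimates using normal approximation".
- Aim 1 defines attrition as having no 2-month assessment, as a fraction of those consented and randomized.

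**The concern.** Attrition, as the plan defines it, removes exactly the participants whose Aim 3b outcome would be missing. An interval that allows for 15% attrition should therefore rest on 17 per arm. The printed intervals looked too narrow for that.

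The overview of the SAP makes interval estimation the main analytic approach and treats the efficacy estimates as one input to deciding whether RLP-MH merits further testing. The three Aim 3b intervals are the only precision figures the plan gives for efficacy. If they ignore attrition, readers are told to expect more precision than the design would deliver under its own assumption. They are also told that .50 versus .20 would give an interval clear of zero even after dropout.

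**Working it through.** **Inputs**

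- Randomized per arm: 20 (Sample size considerations); total 40 (Methods, Overview).
- Attrition: 15% (Sample size considerations). Completers per arm, with equal loss: 20 x 0.85 = 17.
- Yes proportions, RLP-MH and control: .25 and .10; .50 and .20; .60 and .20 (Sample size considerations).
- Method: normal approximation (Aim 3b), 95% level (SAP overview), so the multiplier is 1.96.

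**Formula**

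d ± 1.96 x sqrt[(p1(1-p1) + p2(1-p2)) / n], with n per arm.

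Variance sums, S = p1(1-p1) + p2(1-p2):

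- .25 vs .10: .1875 + .0900 = .2775
- .50 vs .20: .2500 + .1600 = .4100
- .60 vs .20: .2400 + .1600 = .4000

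**Step 1. Reproduce the plan's figures with n = 20 (no attrition)**

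- 1.96 x sqrt(.2775/20) = .231, so .15 ± .231 = (-.081,.381)
- 1.96 x sqrt(.4100/20) = .281, so .30 ± .281 = (.019,.581)
- 1.96 x sqrt(.4000/20) = .277, so .40 ± .277 = (.123,.677)

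All six limits agree with the stated values to two decimals.

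**Step 2. Apply the stated attrition, n = 17**

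- 1.96 x sqrt(.2775/17) = .250, so .15 ± .250 = (-.100,.400)
- 1.96 x sqrt(.4100/17) = .304, so .30 ± .304 = (-.004,.604)
- 1.96 x sqrt(.4000/17) = .301, so .40 ± .301 = (.099,.701)

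| Proportions | Stated | n = 20 | n = 17 |
|---|---|---|---|
| .25 vs .10 | (-.08,.38) | (-.081,.381) | (-.100,.400) |
| .50 vs .20 | (.02,.58) | (.019,.581) | (-.004,.604) |
| .60 vs .20 | (.12,.68) | (.123,.677) | (.099,.701) |

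The half-widths grow by sqrt(20/17) = 1.085.

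**Step 3. Solve the stated half-widths for n**

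n = 1.96² x S / h², with stated half-widths h of .23, .28 and .28:

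- .25 vs .10: 3.8416 x .2775 / .0529 = 20.1 (19.3 to 21.1 if h is .23 ± .005)
- .50 vs .20: 3.8416 x .4100 / .0784 = 20.1 (19.4 to 20.8)
- .60 vs .20: 3.8416 x .4000 / .0784 = 19.6 (18.9 to 20.3)

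The only whole number consistent with all three is 20.

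**Step 4. Look for another route to the stated set**

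- *Other formulas at 17 per arm.* Pooled variance, an n-1 variance, a t quantile, a continuity correction, a 90% level, Agresti-Caffo and Newcombe intervals all fail to reproduce the set.
- *Other numbers.* 18 or 19 per arm fail, and so does loss in one arm only (17 and 20, either way round).
- *20 as the number left after attrition.* This would need 20/0.85 = 23.5, that is 24 per arm and 48 in total, against the stated 20 randomized per arm and 40 in total.
- *The attrition sentence refers to Aim 1.* The completion intervals also use 20: for .60, n = 20 gives (.385,.815), matching the stated (.39,.81), while n = 17 gives (.367,.833). Using 20 is proper there, because the Aim 1 denominator is the number randomized to the intervention. The attrition sentence therefore describes no interval in the paragraph.

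**The case against.** The arithmetic is not in dispute; the case on the other side is about weight. The trial is a 40-person pilot for feasibility and acceptability, with efficacy only explored. The plan contains no hypothesis test, power claim, target width or progression rule tied to these intervals. The examples are illustrative, the limits move by about .02, and the final analysis will use whatever numbers are observed. No text says that 20 per arm was chosen to reach a given Aim 3b width. All of this stands, and it bounds the consequence: planned precision is misstated, but no result or decision rule is corrupted.

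The crossing of zero also deserves restraint. The plan attaches no special meaning to excluding zero, and its first example already includes it without comment. The recomputed lower limit is -.004, which is zero at the plan's two decimals. With 18 per arm it would be +.004. Proportions of .50 and .20 are not whole counts out of 17 (8.5 and 3.4 people): 8/17 versus 3/17 gives a lower limit of -.004, whereas 9/17 versus 3/17 gives +.054. On the other hand, every 95% method tried at 17 per arm with the plan's own proportions puts the lower limit below zero: pooled -.021, n-1 variance -.014, t -.016, continuity-corrected -.063, Agresti-Caffo -.026, Newcombe -.019. The change is real but narrow, and secondary to the widening of all three intervals.

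Finally, less precision follows only if 15% attrition occurs, and attrition is something the pilot sets out to estimate. That is fair, but the plan says the 15% is already in the figures, and it is not.

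An appeal to intent-to-treat does not help. The SAP uses the term to mean assessing outcomes regardless of attendance, and it specifies no imputation for the Yes/No items.

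**Conclusion.** The concern holds. The stated Aim 3b intervals assume complete 2-month follow-up of all 20 per arm, so the claim that they allow for 15% attrition is wrong as written. Under that allowance each half-width is about 8.5% larger (.231 to .250, .281 to .304, .277 to .301). The first interval still includes zero, the third still excludes it, and the second changes from just excluding to just including it.

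This rests on equal loss in the two arms, the plan's normal approximation with unpooled variance, and analysis of observed 2-month responses. The Aim 1 completion intervals are correct and unaffected.

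**What to change.** Restate the three Aim 3b intervals at 17 per arm, keeping the plan's normal approximation: (-.10,.40), (-.004,.604) and (.10,.70). The middle one is better printed to three decimals so that its sign is visible. Replace the closing sentence with one saying that the Aim 3b intervals assume 15% attrition, leaving 17 of 20 per arm with 2-month data, and that the Aim 1 completion intervals use all 20 randomized to RLP-MH.

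The alternative is to keep the printed intervals, delete the attrition sentence and state that complete follow-up is assumed. That is accurate too, but it drops a useful planning assumption, so recomputing is preferable.

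Either way the cost is SAP wording. Recomputing makes the stated precision slightly less favorable. Enrollment, procedures and the analysis method do not change.
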